7.4.9 Control arm – usual care only

Participants in the control group will be provided with

- Documents
 - 1 x usual care information booklet and recording diary.
 - 1 x Moving more with MS booklet
 - 1 x Chartered Society of Physiotherapy – 6 exercises for staying steady booklet

Participants in the control group will continue to receive their usual care provided by their MS team. Participants will attend the clinic for baseline measurements and will complete the same outcome measures and assessments at equivalent timepoints to those in the SNMES arm.

The researcher will show the participant the information booklet and signpost them to the sections regarding the study timeline and key dates to help with planning, importance of completing the measures and recording information related to device use, other physical activity and health resources used and support contact information. They will be advised to continue with their normal exercise and physical activity routines and will continue to receive their usual care.

Consistent with the retention strategy of the study the researcher will discuss the importance of the control arm and implications for drop out.

7.4.10 Nested qualitative studies (semi structured interviews)

7.4.10.1 People with MS and carers

Semi-structured interviews will be conducted via telephone or online depending on the participants preference. Interviews will be exploratory and conversational, guided by flexible topic guides which have been developed with our PPI group.

The topic guides draw upon the Theoretical Framework of Acceptability (TFA)⁴³ and include questions related to experiences of study participation decisions, recruitment and randomisation processes, study arm allocation, perceptions of what outcomes are important, feedback on study information/materials and how to improve them, barriers and facilitators to engaging with the intervention, and any concerns. Interview formats will be considerate of individuals' needs e.g. provision of prior materials in different user-friendly formats, accommodative of fatigue levels (e.g. incorporating a rest break, if desired). Prior to the interviews we will also send people with MS a copy of the questions from the topic guide. The topic guides have been developed with our PPIE group to ensure they are appropriate and accessible to people with MS.

Interviews will be conducted by the research assistant who will be supported by a qualitative researcher on the study team.

Interviews, conducted in a timely manner after the 12-week end-point, were chosen rather than focus groups to minimise recall bias, help engage those who dislike group discussions and facilitate ease of scheduling around participants' availability.

7.4.10.2 Healthcare practitioners and staff involved in the study

Acceptability evaluation will be supplemented by interviews with healthcare practitioners and staff who were involved in the set up and delivery of the study.

Interviews will be conducted by a qualitative researcher from the University of Liverpool. Interviews, conducted in a timely manner during and after recruitment period of the study.

Separate topic guides have been developed, that are similar to those used for people with MS and their carers but also include additional questions related to the practicality of delivering the intervention across settings and recommendations for a future definitive trial. The topic guides have been developed with our PPIE group and clinical partners.

For all groups

All interviews will be audio-recorded using an encrypted Dictaphone, transcribed, anonymised and checked.

8 ADVERSE EVENTS

8.1 DEFINITIONS

Adverse Event (AE): any untoward medical occurrence in a patient or clinical study subject, including unfavourable and unintended signs, including abnormal laboratory results, symptoms or a disease associated with treatment.

Serious Adverse Event (SAE): any untoward and unexpected medical occurrence or effect that:

- **Results in death**
- **Is life-threatening** – refers to an event in which the subject was at risk of death at the time of the event; it does not refer to an event which hypothetically might have caused death if it were more severe
- **Requires hospitalisation, or prolongation of existing inpatients' hospitalisation**
- **Results in persistent or significant disability or incapacity**
- **Is a congenital anomaly or birth defect**

Medical judgement should be exercised in deciding whether an AE is serious in other situations. Important AEs that are not immediately life-threatening or do not result in death or hospitalisation but may jeopardise the subject or may require intervention to prevent one of the other outcomes listed in the definition above, should also be considered serious.

Potential adverse event for this study

- Falls resulting from use of the SNMES machine or associated equipment.
- Muscle or joint injury requiring hospitalisation or attendance at a hospital/ GP or community-based services.

Previous research has identified no adverse events associated with SNMES in MS.⁷⁰

Adverse reactions

Adverse reactions are derived mainly from those associated with exercise interventions in MS. As the SNMES is intended to replicate physiological demands consistent with exercise these have been included here.

- joint pain
- muscle pain or delayed onset muscle soreness
- sprains
- strains
- local muscle fatigue
- central fatigue
- wounds
- illness

Unexpected

The following events have been reported in the literature

- blood pressure spike (n=1 participant) - osteoarthritis population ⁷¹
- Orthostatic events MS (n=2 participants) ⁷²
- superficial burn due to improper configuration (n=1 participant) ^{73 74}

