8.2.2 Serious Adverse Events (SAEs)

Upon identification of an SAE the Principal Investigator should complete a study specific SAE form and sent to the Chief Investigator/Study Team within 24 hours. Relapse and death due to Multiple Sclerosis, and hospitalisations for elective treatment of a pre-existing condition do not need reporting as SAEs.

Contact details for reporting SAEs

Please send SAE forms to: [contact] and [contact]

[contact] (study sponsor) (Mon to Fri 09.00 – 17.00)

All SAEs should be reported to the **<name of REC>** where in the opinion of the Chief Investigator, the event was:

- ‘**related**’, i.e. resulted from the administration of any of the research procedures; and
- ‘**unexpected**’, i.e. an event that is not listed in the protocol as an expected occurrence

Reports of related and unexpected SAEs should be submitted within 15 days of the Chief Investigator becoming aware of the event, using the [HRA Non-CTIMP safety report to REC form](#). The Chief Investigator must also notify the Sponsor of all SAEs.

For NHS REC approved studies please refer to <https://www.hra.nhs.uk/approvals-amendments/managing-your-approval/safety-reporting/> - (Scroll to Safety reporting for non-CTIMP studies).

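### The SAE definition includes 'unexpected', contradicting the protocol's own reporting section; a serious event the protocol foresees could lose SAE status and the 24-hour route

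*Protocol*

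**What the plan says.** Protocol section 8.1 defines an SAE as "any untoward and unexpected medical occurrence or effect that" meets one of a set of seriousness criteria, among them "Requires hospitalisation, or prolongation of existing inpatients' hospitalisation".

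The same section then gives three lists:
- Potential adverse events for this study: "Falls resulting from use of the SNMES machine or associated equipment" and "Muscle or joint injury requiring hospitalisation or attendance at a hospital/ GP or community-based services".
- Adverse reactions, introduced with "Adverse reactions are derived mainly from those associated with exercise interventions in MS". The entries include sprains, strains, wounds and illness, with no limit on severity.
- Events headed 'Unexpected', taken from the literature: a blood pressure spike, orthostatic events and a superficial burn.

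Section 8.2.2 requires a "study specific SAE form and sent to the Chief Investigator/Study Team within 24 hours" once an SAE is identified, and requires the Chief Investigator to tell the sponsor of every SAE. It exempts MS relapse, death due to MS and elective admission for a pre-existing condition. It then narrows REC reporting to SAEs that are both related and unexpected, where unexpected means "an event that is not listed in the protocol as an expected occurrence".

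Section 8.2.1, on non-serious events, requires all adverse events to be recorded whether or not they were expected.

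**The concern.** Seriousness and expectedness answer different questions. Seriousness concerns the outcome of the event and should decide how fast it is escalated. Expectedness concerns whether the event was foreseen and should decide who outside the trial team must be told. Section 8.2.2 keeps the two apart; the definition in 8.1 merges them.

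The merger matters because 8.1 also lists foreseen events, and one of them is described partly by hospitalisation, which is itself a seriousness criterion. An investigator who follows the definition to the letter could decide that such an admission is expected and therefore not an SAE.

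What is at stake is prompt escalation. Participants have an EDSS of 4.0 to 6.5 and use the device at home. The scheduled contacts between baseline and the 12-week visit are calls after week 1 and at week 6. Between those contacts, the SAE rule is the only one with a clock for bringing a serious event to the Chief Investigator.

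**Working it through.** The protocol states no figure on this point, so the check sets its sections side by side and traces events through them.

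**1. Are the two sections consistent?** Under 8.1, SAE = untoward AND unexpected AND serious. Under 8.2.2, REC-reportable = SAE AND related AND unexpected. If the 8.1 definition held, every SAE would already be unexpected and the last condition in 8.2.2 would do nothing. Section 8.2.2 therefore presupposes that some SAEs are expected, which 8.1 rules out.

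**2. A foreseen serious event: a muscle or joint injury leading to admission.**
- Seriousness: met, by the hospitalisation criterion.
- Unexpected: not met, if the 'Potential adverse event' list is taken as the expected list.
- Result under 8.1: not an SAE, so no 24-hour form and no SAE notification to the sponsor. It is recorded as an adverse event only.
- Result with 'and unexpected' deleted: an SAE, with both steps triggered.

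A device-related fall leading to admission, or a serious event classed as 'illness', follows the same path, because those entries carry no severity limit.

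**3. A serious event under the 'Unexpected' heading, or on no list.** All conditions are met. It is an SAE, goes within 24 hours, and goes to the REC if judged related. The definition loses nothing here.

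**4. Do other clauses restore the 24-hour route in case 2?**
- Section 8.2 asks for all adverse events to be reported, but refers each to the procedures that follow it.
- Section 8.2.1 secures a record on the case report form and in the notes. It sits under the non-serious heading and sets no time limit.
- The medical-judgement clause in 8.1 addresses situations other than the listed criteria, and events that did not lead to death or admission. A hospitalised injury is outside its terms.

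None of them supplies the missing step.

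**5. The REC step.** In case 2 the event is not REC-reportable under the 8.1 definition. It is still not REC-reportable after 'and unexpected' is deleted, because 8.2.2 applies its own unexpectedness test. The definition changes the 24-hour and sponsor steps only.

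**The case against.** The strongest reply is that the definition may exclude nothing. The protocol explains 'unexpected' only in 8.2.2, as not being listed as an expected occurrence, and no list carries the heading 'expected'. On that strict reading no event is expected and every serious event stays an SAE. The surrounding text also suggests a slip of wording. The explicit exemptions in 8.2.2 do not include device injuries, and a separate REC filter makes sense only if expected SAEs exist.

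Much of this stands. That the 'Potential adverse event' and 'Adverse reactions' lists are the expected list is inferred from their contrast with the 'Unexpected' heading; it is not stated. It is also true that the events are not lost, since all adverse events must be recorded.

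The reply does not remove the problem. If nothing is listed as expected, the REC filter in 8.2.2 has nothing to work on and the separate 'Unexpected' heading has no purpose. A site cannot tell which reading applies, and the inferred one is natural. Evidence that the authors meant expected serious events to be SAEs is a reason to correct the definition, because sites will work from the definition as written.

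**Conclusion.** The definition is wrong as written and contradicts 8.2.2. Its reach is a defined subset: serious events that 8.1 foresees and that a site treats as expected. For these, the SAE label, the 24-hour form and SAE notification to the sponsor are at risk; the adverse event record is not. The conclusion rests on a literal reading of 8.1 and on the inference that its first two lists are the expected ones. The documents give no event rates, so the number of events cannot be sized.

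Three stronger readings are not supported:
- A reader might infer that serious device-related events in general escape. They do not: unlisted events and those headed 'Unexpected' remain SAEs.
- A reader might blame the definition for listed events not reaching the REC. That follows from the rule in 8.2.2 itself. The fault at that step is that the lists are broad and their status is unclear.
- A reader might infer that SAE counts would be biased in favour of the SNMES arm. Illness, wounds and muscle or joint injury can occur in either arm, and the protocol sets out no between-arm comparison of SAEs. Its progression criteria are consent, retention and adherence.

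**What to change.** 1. Delete 'and unexpected' from the SAE definition in 8.1, so that seriousness alone triggers the 24-hour form and sponsor notification.
2. State in 8.1 that a listed event meeting a seriousness criterion is still an SAE.
3. Reconcile 8.1 with 8.2.2 by saying which list is the expected list, at what severity its entries count as expected, and that it serves the REC test only.
4. Replace the open-ended entries 'illness' and 'wounds' with specific terms.

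Items 1 and 2 repair the 24-hour and sponsor steps. Items 3 and 4 are needed separately for the REC step, which deleting the words leaves unchanged.

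The cost is an amendment to the protocol wording, matching guidance on the SAE form, and possibly a few more SAE forms. The design, sample size and analysis are unaffected.

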8.2 REPORTING PROCEDURES

All adverse events should be reported. Depending on the nature of the event the reporting procedures below should be followed. Any questions concerning adverse event reporting should be directed to the Chief Investigator in the first instance.

8.2.1 Non-serious Adverse Events (AEs)

Adverse Events (AEs) are any untoward medical occurrence in a patient or clinical study subject, including unfavourable and unintended signs, including abnormal laboratory results, symptoms or a disease associated with treatment.

All such events, whether expected or not, should be recorded. All adverse Events will be recorded for your study. These are usually always be recorded on a Case Report Form (CRF) and in the patient's medical notes.

8.2.2 Serious Adverse Events (SAEs)

Upon identification of an SAE the Principal Investigator should complete a study specific SAE form and sent to the Chief Investigator/Study Team within 24 hours. Relapse and death due to Multiple Sclerosis, and hospitalisations for elective treatment of a pre-existing condition do not need reporting as SAEs.

Contact details for reporting SAEs

Please send SAE forms to: [contact] and [contact]

[contact] (study sponsor) (Mon to Fri 09.00 – 17.00)

All SAEs should be reported to the **<name of REC>** where in the opinion of the Chief Investigator, the event was:

- ‘**related**’, i.e. resulted from the administration of any of the research procedures; and
- ‘**unexpected**’, i.e. an event that is not listed in the protocol as an expected occurrence

Reports of related and unexpected SAEs should be submitted within 15 days of the Chief Investigator becoming aware of the event, using the [HRA Non-CTIMP safety report to REC form](#). The Chief Investigator must also notify the Sponsor of all SAEs.

For NHS REC approved studies please refer to <https://www.hra.nhs.uk/approvals-amendments/managing-your-approval/safety-reporting/> - (Scroll to Safety reporting for non-CTIMP studies).

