7.4.4.3 Relapses

A **relapse** is defined as “*a new symptoms or worsening of existing symptoms, causing neurological dysfunction for a minimum of 24 hours without any signs of infection or fever*”.⁵⁵ Exacerbation must be preceded by a stable 4-week period. In these cases, these will be noted by the study team. In the case of relapses, the study neurologist will be consulted and a time for return to the intervention will be agreed by them. Relapses will be confirmed in medical records and by a neurologist.

At each relevant time point e.g. follow up calls (Weeks 1 and 6), 12-weeks and 6-months post randomisation measurements, we will also ask and note if participants had any fluctuations in symptoms or medically confirmed relapses since enrolling on the study. We will additionally review the medical records of participants at the final follow up measure timepoint to identify if they have had any relapses.

¹ Annual relapse rate is calculated for each patient by dividing 365 days with the number of days in the study and multiplying by the number of relapses in the study period

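### Section 8.2.2 exempts relapse from SAE reporting with no explicit relatedness condition, so a serious relapse suspected to be related to SNMES has no expedited route

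*Protocol*

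**What the plan says.** The Protocol's section 8.2.2 asks the site's Principal Investigator, on identifying an SAE, to "complete a study specific SAE form and sent to the Chief Investigator/Study Team within 24 hours". It then lists what is exempt: "Relapse and death due to Multiple Sclerosis, and hospitalisations for elective treatment of a pre-existing condition do not need reporting as SAEs". Two further routes follow in the same section. The first is to the sponsor: "The Chief Investigator must also notify the Sponsor of all SAEs". The second is to the REC within 15 days, for SAEs that the Chief Investigator considers both related to the research procedures and unexpected, the latter meaning "an event that is not listed in the protocol as an expected occurrence".

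Section 8.1 gives the seriousness criteria. They include hospitalisation and "Results in persistent or significant disability or incapacity". Its definition also requires an SAE to be unexpected. Section 8.2.1 covers adverse events in general: "All such events, whether expected or not, should be recorded". It points to the case report form and the medical notes and sets no time limit.

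Section 7.4.4.3 defines a relapse as new symptoms or "worsening of existing symptoms, causing neurological dysfunction for a minimum of 24 hours without any signs of infection or fever", preceded by four stable weeks. Relapses are asked about at weeks 1 and 6, at 12 weeks and at 6 months, and the records are reviewed at the final follow-up. They are confirmed in the medical records and by a neurologist, and the study neurologist agrees when the participant may return to the intervention.

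**The concern.** Exempting events of the disease under study from SAE reporting is common and reasonable. Such an exemption normally stops where the event may have been caused by the intervention, and that limit is not stated here. The words about Multiple Sclerosis confine the exemption for deaths, but they do not clearly confine it for relapses, because a relapse provoked by a study procedure is still an MS relapse.

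At stake is prompt oversight of a home-based intervention used at the highest tolerated intensity. A confirmed relapse that leads to admission or lasting disability, and that the site suspects was brought on by stimulation, is something the Chief Investigator and sponsor should see quickly. Under the present text a site can follow the protocol exactly and send nothing.

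**Working it through.** The protocol states no figure to reproduce on this point. The check is a reading of the safety text, followed by a rough count of events.

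**Following one event through the text.** Take a confirmed relapse in a SNMES participant that requires hospital admission and that the site thinks may be related to stimulation.

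1. Seriousness (section 8.1): the admission meets a listed criterion.
2. Exemption (section 8.2.2): the event is a relapse, so it need not be reported as an SAE. The site is not required to consider relatedness before applying the exemption.
3. Route to the Chief Investigator: the form "sent to the Chief Investigator/Study Team within 24 hours" is for SAEs, so it is not required.
4. Route to the sponsor: this covers all SAEs, so it is not triggered.
5. Route to the REC: the related and unexpected tests are applied to SAEs, so the assessment is not reached.
6. What remains: recording under section 8.2.1, and the steps in section 7.4.4.3. The neurologist's stated role there is to confirm the relapse and agree the time of return. No causality assessment and no deadline is given in either section.

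**Expectedness.** Relapse is on none of the lists of events in section 8.1, but section 7.4.4.3 plans for it in advance. Whether it counts as expected is therefore arguable. This affects the remedy: because section 8.1 builds unexpectedness into the SAE definition, simply limiting the exemption to unrelated relapses could still leave a related one outside the definition.

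**Size.** From the protocol: 25 participants in the SNMES arm (section 7.4.1) and a 12-week programme (section 7.4.8). Assumed, because the protocol gives neither: 0.1 to 0.5 relapses per person-year, of which 5% to 25% are serious.

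- Exposure: 25 × 12/52 = 5.8 person-years.
- Relapses during stimulation: 5.8 × 0.1 = 0.6, up to 5.8 × 0.5 = 2.9.
- Serious relapses: 0.6 × 0.05 = 0.03, up to 2.9 × 0.25 = 0.7.

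The documents give no basis for the share that would be judged related, so none is estimated. Loss to follow-up is ignored. The count does not cover relapses after stimulation ends, or relapses in either arm attributed to another procedure such as the exercise tests.

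**The case against.** The strongest reply is grammatical. Relapse and death can be read as one phrase, with the words about Multiple Sclerosis qualifying both, so that a relapse attributed to SNMES falls outside the exemption. That reading is possible and shows that the text is ambiguous. It does not remove the gap, because a provoked relapse is still a relapse of MS, and two sites could apply the sentence differently.

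The second reply is that relapses are overseen anyway. This is largely true. A reader might infer that serious relapses go unseen, or that a site could exempt any worsening by calling it a relapse. The documents support neither: relapses are asked about, recorded and confirmed by a neurologist, and reactions listed separately in section 8.1, such as central fatigue and muscle pain, are not exempt if serious. What is missing is the deadline, the causality judgement and notification of the sponsor.

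The third reply is that the exemption is permissive and that section 8.1 calls for medical judgement. An investigator may indeed still file a form. But the judgement clause concerns whether an event is serious, and it does not override the exemption or oblige anyone to report.

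**Conclusion.** The point stands as a small gap in safety reporting. Followed as written, section 8.2.2 allows a confirmed, serious relapse suspected to be related to SNMES or another study procedure to bypass the Chief Investigator's 24-hour route, the sponsor and the REC assessment.

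Two stronger readings do not hold. A reader might infer that a reportable event would be withheld from the REC. Expectedness is arguable, so the text shows only that the assessment is skipped, not that a report would be due. A reader might also count events over the full 6 months of follow-up: 25 × 0.5 = 12.5 person-years, giving up to 12.5 × 0.5 × 0.25 = 1.6 serious relapses. Stimulation lasts 12 weeks, so the figure for events during stimulation is about 0.03 to 0.7, with related events a subset.

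That range rests entirely on the assumed relapse rates and serious fractions. The conclusion about the text does not depend on it. Only safety oversight is affected. The consent, retention and adherence estimates and the progression criteria are unchanged.

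**What to change.** Keep the three exemptions in section 8.2.2 and add one clause: except that a relapse meeting a seriousness criterion and judged possibly related to SNMES or a study procedure is reported as an SAE within 24 hours, whether or not relapse is regarded as expected.

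The closing words are needed because of the SAE definition in section 8.1. With them, expectedness matters only for the REC step, where the Chief Investigator already decides it. Deaths due to MS, elective admissions and unrelated relapses stay exempt.

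The cost is one clause and one relatedness judgement for each serious relapse. Under the assumed rates, that is fewer than one expected in the SNMES arm during stimulation, plus any later in follow-up or in the control arm. No visit, form or analysis has to be added.
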